## Statistical analysis

We performed the analysis after the intention-to-treat protocol, and we involved all participants who were randomly assigned [21]. In cases of missing data, the last observation was carried forward. The statistician was masked to the study groups. The absolute risk of TS and its intensity were evaluated by using Fischer's exact test. ( $\alpha = 0.05$ ). The authors calculated the relative risk as the confidence interval for the effect size.

Comparison of the TS intensity (NRS data) of the 2 groups at the 2 different assessment points were performed by using the Mann-Whitney U test, and comparisons between times within each group were performed using the Friedman test. The comparisons of the TS intensity obtained with the VAS scale were evaluated by using a 2-way repeated measures ANOVA and Tukey's test.

Color changes between groups ( $\Delta$ SGU between base line versus 1 week after the 2nd bleaching session) were compared by using a t test, and the shade changes were evaluated by using Student's t test. In all statistical tests, the significance level was 0.05. We performed all analyses by using the software SPSS for windows version 20.0 (IBM).

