minute applications for both groups in accordance with the manufacturer's directions. The bleaching agent was refreshed every 8 minutes during the 24-minute application period. At the end of each session, a single researcher responsible for the blinding [name] delivered a single syringe to the operator, which would contain desensitizing gel if the patient was in the control group, or placebo gel containing only carbopol (no active ingredient) if the patient was in the dexamethasone group. The gel was applied with a brush on the labial surface of the whitened teeth for 2 to 3 minutes as the manufacturer (Soothe SDI Dental Limited) directed. Two bleaching sessions were performed 1 week apart.

TS evaluation: TS was evaluated during bleaching and up to 1 hour, 24 hours and 48 hours postbleaching. The volunteer was asked to indicate the numeric value of the degree of sensitivity for each of the periods above, using a 5-point numeric rating scale (NRS) in which 0= none, 1= mild, 2= moderate, 3= considerable and 4= severe [2,4,5,7,23].

In addition, the volunteers were also instructed to record the pain intensity using the visual analogic scale (VAS) [3,6-9]. This scale is a 100-milimeter horizontal line with scores of 0 and 100 at their ends, in which 0 = no sensitivity and 100 = severe sensitivity. The volunteer had to mark with a vertical line across the horizontal line of the scale the intensity of the TS. Then, the distance in millimeters from the zero ends was measured with the aid of a millimeter ruler.

The data from each bleaching session were evaluated separately and were merged. For this purpose, the worst score or numeric value obtained in both bleaching sessions was considered for statistical purposes and the determination of the overall risk and intensity of TS.

If the volunteer scored 0 (no sensitivity) in all time assessments from both bleaching sessions, this volunteer was considered to be insensitive to the bleaching protocol. In all other circumstances, the volunteers were considered to have sensitivity stemming from the bleaching procedure. This dichotomization allowed us to calculate the absolute risk of TS, which represented the percentage of volunteers who reported TS at least once during treatment. We also calculated the overall TS intensity.

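### Tooth-sensitivity intensity is assigned to Fisher's exact test in one sentence and to other tests in the next paragraph, so the overall worst-score intensity has either two tests or only one that ignores score order

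*Combined protocol and SAP*

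**What the plan says.** All references are to the combined protocol and SAP.

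- **Statistical analysis, first paragraph:** "The absolute risk of TS and its intensity were evaluated by using Fischer's exact test", at a 5% level.
- **Statistical analysis, second paragraph:** "Comparison of the TS intensity (NRS data) of the 2 groups at the 2 different assessment points were performed by using the Mann-Whitney U test". Friedman's test is named for change over time inside an arm. For the other scale: "The comparisons of the TS intensity obtained with the VAS scale were evaluated by using a 2-way repeated measures ANOVA and Tukey's test".
- **Materials and Methods, TS evaluation:** two intensity scales are used. One is a "5-point numeric rating scale (NRS) in which 0= none, 1= mild, 2= moderate, 3= considerable and 4= severe". The other is the VAS: "This scale is a 100-milimeter horizontal line with scores of 0 and 100 at their ends". The worst value over the two sessions is taken for "determination of the overall risk and intensity of TS". A volunteer with zero at every assessment is classed as insensitive and everyone else as sensitive. That split is described as the route to absolute risk, and overall intensity is then mentioned as a further calculated quantity.
- **Results and Tables 2-4:** Fisher's test is named only under the yes/no Table 2. Tables 3 and 4 give intensity by time point within each session. No table or sentence gives a between-group result for overall worst-score intensity.

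**The concern.** Fisher's test suits the yes/no primary outcome. Intensity is a different kind of variable: an ordered 0-4 score or a length in millimetres. The documents give no cut-off that would turn either into the categories of a 2x2 table, so the sentence leaves open what was tested and how.

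The yes/no outcome sits near its ceiling. The sample size paragraph assumes about 90% of controls have some pain, and Table 2 shows 33/35 = 94% and 28/35 = 80%. How bad the pain was therefore carries useful information. The worst score is the plan's only per-patient summary of severity across both sessions. If its test ignores order, a general shift towards milder pain is harder to detect. If it has two candidate tests, the rule does not fix which result counts.

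**Working it through.** **1. Two readings, both faulty.** The documents give no numerical result for overall intensity, so there is no figure to reproduce. The text has to be read side by side.

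- *Reading A: intensity means the same thing in both paragraphs.* Then NRS intensity has both Fisher and Mann-Whitney, and intensity as a whole has three between-group methods, with no order of precedence.
- *Reading B: Fisher covers the merged worst score, and the second paragraph covers the assessment points.* Then no quantity has two tests, but overall intensity has only Fisher's test, and no result for it appears.

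**2. Fisher's test ignores the order of the scores.** Take an illustrative 2x5 table with 35 per arm, scores 0 to 4 (these counts are not trial data):

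| | 0 | 1 | 2 | 3 | 4 |
|---|---|---|---|---|---|
| Control | 5 | 10 | 11 | 6 | 3 |
| Dexamethasone | 11 | 13 | 7 | 3 | 1 |

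- Pairs in which dexamethasone is lower: 10×11 + 11×24 + 6×31 + 3×34 = 662.
- Tied pairs: 5×11 + 10×13 + 11×7 + 6×3 + 3×1 = 283.
- U = 662 + 283/2 = 803.5, against a null mean of 35×35/2 = 612.5.
- Column totals are 16, 23, 18, 9 and 4, so Σ(t³ − t) = 22,818. The variance is (1,225/12) × (71 − 22,818/4,830) = 6,766, SD 82.25.
- z with continuity correction = (191 − 0.5)/82.25 = 2.32, two-sided p = 0.021.
- Fisher's test on the same table (Freeman-Halton, Monte Carlo): p about 0.25.

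Now reorder the columns to 3, 5, 11, 6, 10 against 1, 11, 7, 3, 13. Fisher's p stays at about 0.25. U becomes 471 + 283/2 = 612.5, exactly the null mean, so the Mann-Whitney p becomes 1.0. Fisher's test cannot tell the two orderings apart.

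**3. What this could cost in power.** The documents do not print worst-score counts, so the control distributions are assumptions. Four were used for scores 0 to 4:

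- .10, .45, .25, .15, .05
- .10, .35, .30, .15, .10
- .06, .50, .25, .13, .06
- .10, .60, .20, .07, .03

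Under proportional odds, each cumulative odds is multiplied by the odds ratio (OR). For the first distribution at OR 3, the cumulative probabilities .10, .55, .80, .95 have odds .111, 1.222, 4, 19. These become .333, 3.667, 12, 57, giving .25, .536, .137, .060, .017 in the dexamethasone arm.

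Simulated power, 35 per arm, two-sided 5%, range over the four distributions:

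| OR | Fisher (Freeman-Halton) | Mann-Whitney |
|---|---|---|
| 3 | 39-47% | 59-68% |
| 4 | 60-68% | 80-87% |
| 6 | 83-91% | 95-98% |

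Both tests held about 5% under the null. Two reference points for the OR scale:

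- The odds of no sensitivity in Table 2 are 7/28 = 0.25 and 2/33 = 0.061, a ratio of 4.1.
- With 10% of controls at zero, OR 6 gives odds (0.10/0.90)×6 = 0.667, that is 40% at zero, which is the planned fall from 90% to 60%.

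**4. Other effect shapes.**

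- First distribution, with mild pain becoming none (.40, .15, .25, .15, .05): Fisher 83%, Mann-Whitney 25%.
- Second distribution, with score 3-4 pain becoming mild (.10, .60, .30, 0, 0): Fisher 85%, Mann-Whitney 66%.

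The direction of the power difference therefore depends on how the treatment acts.

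**The case against.** The best defence is Reading B. The Mann-Whitney sentence is tied to assessment points, the overall quantity is defined separately, and so there need be no contradiction. That is a fair reading, but the text does not state it, and it leaves overall intensity with an order-blind test and no reported result. A slip of wording is also plausible, in which case the sentence still needs correcting.

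Several stronger conclusions are tempting, and the documents do not support them.

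- *That overall intensity is the only planned comparison able to separate mild from severe pain.* It is not. The Mann-Whitney and ANOVA comparisons also use severity, and Tables 3 and 4 report between-group comparisons at four times in each session on both scales.
- *That VAS values go to Fisher's test and collapse to the yes/no result.* The plan names ANOVA for VAS intensity. An exact collapse would also require all non-zero readings to be untied, which is unlikely with lengths read off a millimetre ruler.
- *That Fisher's test was in fact misapplied.* No printed intensity result is attributed to it, and the layouts of Tables 3 and 4 fit the tests in the second paragraph.
- *That the analyst chose a test to favour one arm.* The statistician was masked to group. Masking does not remove the ambiguity, but it limits that route to bias.
- *That the trial lost a fixed amount of power.* Step 4 of the working shows that the sign of the difference depends on the effect shape.

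**Conclusion.** The point holds: the analysis rule is wrong as written, for a secondary outcome. On one reading intensity has competing tests. On the other, the merged worst score has only a test that discards the order of its categories. On both, no overall-intensity result is reported.

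The illustrative size is roughly 15-25 percentage points of power lost at OR 3 to 4. It rests on a proportional-odds shift, assumed worst-score distributions and 35 per arm. It narrows at OR 6 and reverses under the two other shapes examined. The stronger ground for a change is that the scale is ordered and the question is whether pain was milder, which an ordinal test addresses directly. The point leaves the choice of Fisher's test for the yes/no primary outcome untouched, and it does not show any printed intensity comparison to be wrong.

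**What to change.** - Remove the reference to intensity from the Fisher sentence, so that Fisher's test covers only the yes/no risk.
- State that overall intensity on the NRS is each volunteer's worst score over both sessions, compared between groups by a two-sided tie-corrected Mann-Whitney test.
- Report an effect estimate with its 95% CI, for example the probability that a dexamethasone score is lower than a control score, counting ties as half (803.5/1,225 = 0.66 in the illustration), together with the 2x5 table of counts.
- Name one test, rank-based or mean-based, for worst VAS.
- Keep the planned assessment-point comparisons, and say that they are separate from the overall result.

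The cost is a sentence or two in the Statistical analysis section and one re-run on data already held, with no new patients or measurements. The downside is some loss of sensitivity to differences that are not a general shift, as step 4 of the working shows. The printed counts let a reader see such a pattern.

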Two calibrated investigators ([name]) independently performed the color evaluations with the shade guide. The 2 examiners, blinded to the allocation assignment, schedule the volunteers for bleaching and evaluated their teeth against the shade guide at baseline and 1 week after the procedure. The 2 examiners were required to have an agreement of at least 85% (Kappa statistic test) before beginning the study evaluation.

Volunteers with anterior restorations or dental prostheses, with anterior orthodontic apparatuses or with severe internal tooth discoloration (tetracycline stains, fluorosis, pulpless teeth) were not included in the study. In addition, pregnant and lactating women, participants with any other pathology that could cause sensitivity (such as gingival recession, dentinal exposure, visible cracks in teeth), those taking anti-inflammatory or analgesic drugs, those who smoked or volunteers who had undergone tooth-whitening procedures were excluded. Those who reported past or present health problems in the stomach, heart, kidneys or liver; those who reported the continuous use of anti-

inflammatory or analgesic drugs; those patients with diabetes, hypertension or the use of antihypertensive drugs; or patients who reported allergies to dexamethasone and lactose were also excluded from the study.

Sample size calculation: The primary outcome of this study was the absolute risk of TS. The absolute risk of TS (that is, the number of patients [percent] who reported pain at some point during dental bleaching) was reported to be approximately 90% for a similar 35% hydrogen peroxide bleaching product [20,21,36]. Thus, a minimum sample size of 70 participants was required to have a 90% chance of detecting, as significant at the 2-sided 5% level, a decrease in the primary outcome measure from 90% in the control group to 60% in the experimental group.

Random sequence generation and allocation concealment: The authors used blocked randomization (block sizes of 2 and 4) with an equal allocation ration, using a 3rd-party service (Sealed Envelope), which did not intervene in the study. Opaque and sealed envelopes containing the identification of the groups were prepared.

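### Fisher's exact test is valid but conservative for the primary outcome at 35 per arm; one named unconditional exact test with a matching interval would gain 6 to 9 points of power

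*Combined protocol and SAP*

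**What the plan says.** The paragraph on sample size, under Materials and Methods, states: "The primary outcome of this study was the absolute risk of TS". It takes a control risk that "was reported to be approximately 90% for a similar 35% hydrogen peroxide bleaching product" and says that "a minimum sample size of 70 participants was required to have a 90% chance of detecting" "a decrease in the primary outcome measure from 90% in the control group to 60% in the experimental group", "as significant at the 2-sided 5% level".

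The Statistical analysis section then gives the test: "The absolute risk of TS and its intensity were evaluated by using Fischer's exact test", with alpha 0.05. The effect measure follows: "The authors calculated the relative risk as the confidence interval for the effect size". The section does not name an interval method. It also has no sentence on what happens if the interval and the test point in different directions.

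In the Results (Tooth Sensitivity), the significance statement rests on the p-value. The relative risk and its 95% interval are then cited as further evidence of no effect. The footnote to Table 2 names only Fisher's test.

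**The concern.** A conditional exact test and a relative-risk interval are not inversions of one another, so they can give different answers on the same table. The chance of this is greatest where the data are discrete and risks are near the boundary. This trial is in that position, with 35 per arm and a control risk near 90%.

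Two things are at stake. First, Fisher's test may use much less than the two-sided 5% allowed, which costs power in a small trial whose non-significant result is read as no effect. Second, a report could show a non-significant p-value beside an interval that excludes 1, with nothing in the plan to tell the reader how to take the pair.

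**Working it through.** **Inputs.** 70 volunteers allocated equally, so 35 per arm (Table 2: 33 + 2 and 28 + 7). Planned risks 90% and 60%, two-sided 5%. The 90% v 70% and 94% v 80% cases are added as smaller effects; the second is close to the observed 33/35 and 28/35.

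**The plan's own figure.** The pooled normal formula gives n per arm = [1.960·√(2·0.75·0.25) + 1.282·√(0.9·0.1 + 0.6·0.4)]² / 0.30² = (1.200 + 0.736)² / 0.09 = 41.7, so 42 per arm or 84 in total. At 35 per arm the same approximation gives Φ[(0.30·√35 − 1.200)/0.574] = Φ(1.00) = 84.1%. The stated 90% at 70 is therefore not reproduced. That is a separate matter and serves here only as a reference point.

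**Fisher's test.** Let a and b be the numbers with sensitivity in the control and dexamethasone arms. For each of the 36 × 36 tables, p_F(a,b) is the sum of the hypergeometric probabilities, given a + b, that do not exceed that of the table itself. With R the set where p_F ≤ 0.05,

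Pr(reject; π₁, π₂) = Σ over R of Bin(a; 35, π₁) · Bin(b; 35, π₂).

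Setting π₁ = π₂ gives the size: 1.3% at 0.90, 0.4% at 0.94, and a maximum of 2.9% over all common risks.

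**Boschloo's test.** Order the tables by two-sided p_F and set p_B(a,b) = max over π of Pr(p_F(A,B) ≤ p_F(a,b); π, π), here over a 499-point grid. Fisher's p-value is conservative at every π, so p_B ≤ p_F, and every table that Fisher rejects is also rejected by Boschloo. The maximum size is 4.8%. A pooled-z unconditional exact test, built the same way from the pooled z statistic, also has maximum size 4.8%.

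| True risks | Fisher | Boschloo | Pooled-z exact |
|---|---|---|---|
| 90% v 60% | 78.5% | 84.9% | 85.2% |
| 90% v 70% | 45.5% | 54.2% | 56.1% |

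Boschloo gains 84.9 − 78.5 = 6.4 points and 54.2 − 45.5 = 8.7 points. For scale, Fisher's test reaches 85.2% at 90% v 60% only with 40 per arm.

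**The interval (method assumed).** Log method: RR = b/a, SE = √(1/a + 1/b − 2/35), limits RR·exp(±1.96·SE). The probability that this interval excludes 1 while two-sided Fisher is non-significant is:

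| True risks | Share of trials |
|---|---|
| 90% v 90% | 3.0% |
| 90% v 85% | 4.3% |
| 90% v 80% | 7.4% |
| 90% v 70% | 10.6% |
| 90% v 60% | 6.5% |
| 94% v 80% | 12.6% |

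The reverse occurs in 60 tables. All have no events in one arm, where the log interval cannot be formed, and their probability at these risks is below 10⁻¹³.

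**One volunteer from the observed data, 33 v 27.** RR = 27/33 = 0.818; SE = √(0.0303 + 0.0370 − 0.0571) = 0.101; interval 0.67 to 0.997, which excludes 1. Fisher p = 0.084, pooled-z exact p = 0.043, Boschloo p = 0.052.

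**Observed data, 33 v 28.** RR = 28/33 = 0.848; SE = √(0.0303 + 0.0357 − 0.0571) = 0.094; interval 0.71 to 1.02. Two-sided p-values: Fisher 0.151, Boschloo 0.11, pooled-z exact 0.086. All are non-significant. (The printed 0.075 matches the one-sided Fisher value, 0.0753.)

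**The case against.** The case for leaving the plan alone is substantial, and much of it stands.

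- **Fisher's test is valid.** A reader might infer from a size of 1.3% that the test has the wrong error rate. It does not. Alpha 0.05 is an upper bound, Fisher respects it throughout, and the documents nowhere claim an attained size of 5%. The cost is power only.
- **The deciding test can be identified.** A reader might infer that nothing says which result counts. No explicit precedence sentence exists, but the Statistical analysis section gives the 5% level to Fisher and the relative risk to effect size, and the Results follow that order.
- **Disagreement depends on the scenario.** A reader might take 7% to 13% as a general rate. That range fits only some situations in which the risks differ; with both risks at 90% it is 3.0%.
- **The interval method is assumed.** The interval printed in Table 2, 0.24 (0.05 to 1.26), is numerically an odds ratio: (28 × 2)/(7 × 33) = 0.242. Against a Wald odds-ratio interval, disagreement with Fisher is 0.5% at 90% v 90%, 6.3% at 90% v 60% and 3.8% at the observed rates. At 33 v 27 the odds-ratio interval is 0.04 to 1.04, so that example no longer splits. The figures above describe the relative-risk interval that the plan specifies, not the one printed.
- **This trial's conclusion is unchanged.** Every two-sided test checked is non-significant on 33 v 28.

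The power comparison survives all of this. It does not depend on the interval method: at the same 70 volunteers and two-sided 5% level, Boschloo's test rejects everything that Fisher's does, and more.

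**Conclusion.** The point holds as a low-cost improvement. With 35 per arm and risks near 90%, Fisher's test gives up 6.4 points of power at the planned effect and 8.7 points at 90% v 70%, compared with a test that also holds the two-sided 5% level. These figures rest only on the planned risks, equal arms of 35 and independent binomial counts.

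The mismatch between test and interval is a secondary matter. It amounts to 3.0% to 12.6% of trials in the scenarios shown, and only if the unnamed interval is the log-method relative-risk interval. The documents do not support a claim of inflated type I error, of an undefined primary test, or of a different conclusion in this trial.

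**What to change.** Name one test and draw the intervals from it. Suggested wording:

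*The primary comparison uses Boschloo's two-sided unconditional exact test at 5%; the risk difference and relative risk are reported with 95% confidence intervals obtained by inverting that same test; Fisher's exact test is a sensitivity analysis.*

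Do not leave a choice between pooled-z and Boschloo. They fall on opposite sides of 5% at 33 v 27 (0.043 v 0.052), so an open choice would bring back the possibility of two verdicts.

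The data are already unblinded, so here the analysis should be reported only as a labelled sensitivity analysis, with Fisher's two-sided result kept as the planned one.

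The cost is one sentence and a short run. The downside is a less familiar test, which may need software other than the package named in the Statistical analysis section. If Fisher is kept, the minimum is to name the interval method and state that Fisher's test decides. That removes the ambiguity but does not recover the power.

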Color evaluation: Shade evaluation was performed before 1 week after the 1st bleaching session, but before the 2nd session, and 1 week after the 2nd bleaching session. Color evaluation was not performed immediately after each bleaching session so that the effect of dehydration and demineralization on color measures could be avoided. We performed the color evaluation using the shade guides of VITA Classical and the VITA Bleachedguide 3D-MASTER. (VITA Zahnfabrik).

For the color evaluation, the VITA Classical shade guide's 16 tabs were arranged from highest (B1) to lowest (C4) value. Although this scale is not linear in the truest sense, we treated the changes as representing a continuous and approximately linear ranking for the purpose of analysis, as already performed in several published studies [2,3,5,8,9,15,23,25]. The VITA Bleachedguide 3D-MASTER contains lighter shade tabs and is already organized from the highest (0M1) to lowest (5M3) value [24]. The measurement area of interest for shade matching was the middle 1/3 of the facial surface of the central incisor, according to the American Dental Association guidelines [4,12,15].

The 2 examiners, masked to the allocation assignment, scheduled the volunteers for bleaching and evaluated their teeth against the shade guide at the different time assessments. Color changes were calculated from the beginning of the active phase up to and including recall times by calculating the change in the number of shade guide units ( $\Delta$ SGU), which occurred toward the lighter end of the value-oriented list of shade tabs. In the event of disagreements between the examiners during shade evaluation, a consensus was reached through discussion.

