#### Results

We screened 123 participants examined in the dental chair to check if they met the inclusion and exclusion criteria (Figure 1). The bleaching procedures were implemented exactly as planned and no modification was performed.

Characteristics of included participants: The baseline color of the volunteers was similar (control group: 5.9 [1.9]; dexamethasone: 5.6 [2.1]); the mean age (SD) between volunteers was similar between the groups (control: 22.5 [2.1] and dexamethasone: 22.3 [2.7]), ranging from 19 to 29 years. Thirty-four percent of the volunteers from the control group, and 23% of the volunteers from the dexamethasone group were men.

*Protocol adherence and dropouts*: No discontinuity in both treatment groups was found in the clinical investigation. All volunteers attended the recall visit 1 week postbleaching.

*Tooth Sensitivity*: Two volunteers, 1 from each group, took an analgesic to alleviate the bleaching-induced TS (Tylenol, Janssen Cilag Farmacêutica) in the period from 5 to 7 hours after the 2nd and last clinical bleachings.

Table 2 shows the number of participants who experienced TS during the bleaching regimen in the control group and dexamethasone group. In this table, it is shown that no significant difference was observed between groups (p = 0.075). The relative risk, along with the 95% confidence interval, is also evidence that the use of the experimental drug protocol had no effect on the reduction of TS.

Tables 3 and 4 show that the TS was similar in both groups, at different assessment points, in both sessions, using both pain scales. It is also seen that the bleaching-induced TS did not last longer than 48 hours after the bleaching protocol (Tables 3 and 4).

Color Evaluation: Significant whitening was observed in both groups (P < .001). The descriptive data from bleaching obtained after the 1st and 2nd bleaching sessions can be seen in Table 5. At the end of the bleaching protocol, a whitening of approximately 3 shade guide units was detected for both groups.

The results of the subjective shade evaluation (VITA Classical: P = 0.27; VITA Bleachedguide 3D-MASTER: P = 0.68) matched the hypothesis of equality between the groups after bleaching. The effect size and the confidence interval for the overall mean difference is also shown in Table 5 and is evidence of no statistical difference between groups.

Adverse effects: In this study, no reports of adverse effects by volunteers were received.

TABLE 1

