During bleaching	8.09 (17.06) AB	7.51 (15.46) A	NS†	14.03 (21.39) A	6.46 (6.34) AB	NS†
Up to 1h after bleaching	11.14 (20.08) A	6.31 (12.78) A	NS	14.31 (20.13) A	7.57 (13.46) A	NS
Up to 24h after bleaching	8.26 (13.48) A	5.06 (9.86) A	NS	16.60 (21.57) A	9.77 (20.55) A	NS
Up to 48h after bleaching	2.91 (9.14) B	0.37 (1.54) B	NS	1.91 (5.46) B	1.14 (4.46) B	NS

\* Within each column, significant differences are represented by different uppercase letters.

† NS: No significant difference between groups.

TABLE 5

Means (standard deviations) of the change in shade guide units obtained with the VITAL Classical\* and VITA Bleachedguide 3D-Master\* at baseline versus each bleaching session and 1 week post-bleaching.

COLOR	GRO	DUPS		MEAN DIFFERENCE
EVALUATION TOOL	Control	Dexamethasone	P VALUE	(95% CONFIDENCE INTERVAL)
VITA Classical	2.14 (1.52)	1.89 (1.37)	0.46	0.35 (-0.43-0.95)
VITA Bleachedguide	1.91 (0.95)	1.86 (0.97)	0.81	0.06 (-0.40-0.52)
VITA Classical	0.74 (1.15)	0.71 (1.49)	0.93	0.03 (-0.61-0.66)
VITA Bleachedguide	1.29 (0.52)	1.23 (0.69)	0.70	0.06 (-0.23-0.35)
VITA Classical	2.54 (2.39)	2.91 (1.96)	0.48	-0.37 (-1.42-0.67)
VITA Bleachedguide	3.00 (1.19)	3.2 (1.35)	0.51	-0.20 (-0.81 -0.41)
VITA Classical	2.77 (1.96)	2.26 (1.87)	0.27	0.51 (-0.40-1.43)
VITA Bleachedguide	3.20 (1.13)	3.09 (1.17)	0.68	0.11 (-0.44 – 0.66)

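### The between-arm colour comparison uses baseline shade only by subtraction; a post hoc baseline-adjusted ANCOVA on data already held would probably narrow the interval, though the documents cannot prove it

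*Combined protocol and SAP*

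**What the plan says.** The Statistical analysis section states that the changes in shade guide units "between base line versus 1 week after the 2nd bleaching session) were compared by using a t test". It names no covariate and no adjusted model, and neither does any other section or Table 5.

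Baseline shade is available. In Materials and Methods the two examiners "evaluated their teeth against the shade guide at baseline and 1 week after the procedure", and the Color evaluation paragraph derives the outcome "by calculating the change in the number of shade guide units". That subtraction is the only use made of baseline. The same paragraph acknowledges the nature of the scale: "Although this scale is not linear in the truest sense, we treated the changes as representing a continuous and approximately linear ranking".

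The Results give baseline shade by arm ("control group: 5.9 [1.9]; dexamethasone: 5.6 [2.1") without saying which of the two guides the figures belong to. For the final comparison on VITA Classical, Table 5 reports a mean difference and interval of "0.51 (-0.40-1.43"), and the text concludes that the shade results "matched the hypothesis of equality between the groups after bleaching".

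**The concern.** In a randomised comparison, a t test on change and an ANCOVA with baseline as covariate both estimate the treatment difference without bias. They differ in precision. The change score forces the baseline coefficient to be 1, whereas ANCOVA estimates it. ANCOVA therefore gives a tighter interval unless baseline is almost uncorrelated with change.

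There is reason here to expect some correlation. Volunteers with A1 teeth were eligible, and A1 is among the lightest tabs on the VITA Classical guide, so those volunteers had little room to lighten on it.

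What is at stake is modest. Colour is not the primary outcome, which is the absolute risk of tooth sensitivity. But the paper's statement about equal whitening rests on the colour interval, and an upper limit of 1.43 units is wide against mean changes of 2.77 and 2.26. A tighter estimate would describe the between-arm difference better. It would not establish equality, because no margin is stated.

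**Working it through.** **Inputs.**
- 35 per arm (Table 2), with no dropouts (Results).
- Final change, VITA Classical (Table 5): control 2.77 (SD 1.96), dexamethasone 2.26 (SD 1.87).
- Final change, Bleachedguide (Table 5): 3.20 (1.13) and 3.09 (1.17).
- Baseline (Results): 5.9 [1.9] and 5.6 [2.1], guide not named.
- Not given: r, the within-arm correlation between baseline and change (positive when darker teeth lighten more). It is varied from 0 to 0.7 for interval width, and over its whole range for significance.

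**Pooled SDs.**
- Classical change: √[(1.96² + 1.87²)/2] = 1.916
- Bleachedguide change: √[(1.13² + 1.17²)/2] = 1.150
- Baseline: √[(1.9² + 2.1²)/2] = 2.002

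**Reproducing the reported result.** SE = 1.916 × √(2/35) = 0.458. Half-width = t(0.975; 68) × SE = 1.995 × 0.458 = 0.914. The interval is 0.51 ± 0.914, that is −0.40 to 1.42, with P = 0.27. Table 5 gives −0.40 to 1.43 and P = 0.27, so the published analysis is the unadjusted t test. For the Bleachedguide the t-test half-width is 0.549.

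**Baseline balance.** The gap is 5.9 − 5.6 = 0.30, or 0.15 SD, with 95% CI −0.66 to 1.26 and P = 0.53. It gives no reason to suspect bias.

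**ANCOVA half-width.** With g the baseline gap in SD units:

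half-width = t(0.975; 67) × √[ (68/67) × SD² × (1 − r²) × (2/35 + g²/68) ]

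Because the guide for 5.9 and 5.6 is not named, g is varied from 0 to 0.3.

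| Guide (t test) | g | r = 0 | r = 0.3 | r = 0.5 | r = 0.7 |
|---|---|---|---|---|---|
| Classical (0.914) | 0 | 0.921 | 0.878 | 0.797 | 0.658 |
| Classical | 0.15 | 0.923 | 0.881 | 0.800 | 0.659 |
| Classical | 0.3 | 0.931 | 0.888 | 0.807 | 0.665 |
| Bleachedguide (0.549) | 0 | 0.553 | 0.527 | 0.479 | 0.395 |
| Bleachedguide | 0.3 | 0.559 | 0.533 | 0.484 | 0.399 |

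The size of the gap hardly matters. Setting the ANCOVA half-width equal to the t-test half-width gives a break-even |r| of 0.123, 0.145 and 0.194 at g = 0, 0.15 and 0.3.

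**How plausible is a small r?** Assume that 5.9 and 5.6 are VITA Classical units. Then

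final SD = √(2.002² + 1.916² − 2 × r × 2.002 × 1.916)

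- r = 0 implies a final SD of 2.77, against 2.00 at baseline.
- r = −0.145 and r = 0.145 imply 2.96 and 2.56. The interval therefore fails to narrow only if the final SD is 28% to 48% above the baseline SD.
- If the spread stayed at 2.00, r = 1.916/(2 × 2.002) = 0.48 and the half-width is 0.81.

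On the same assumption the final means are 5.9 − 2.77 = 3.13 and 5.6 − 2.26 = 3.34, close to the light end of the guide. A marked increase in spread is therefore possible but not what one would expect.

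**Would the conclusion change?** On the same assumption, adjusted difference = 0.51 − r × (1.916/2.002) × 0.30:

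| r | Adjusted difference (95% CI) | P |
|---|---|---|
| 0.3 | 0.42 (−0.46 to 1.30) | 0.34 |
| 0.5 | 0.37 (−0.43 to 1.17) | 0.36 |
| 0.7 | 0.31 (−0.35 to 0.97) | 0.35 |

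P falls below 0.05 only if r is below −0.65 or above 0.97 (final SD above 3.56 or below 0.50). Allowing the rounded gap to lie between 0.2 and 0.4, the thresholds range from −0.71 to −0.60 and from 0.93 to 0.99. No adjusted Bleachedguide difference is given, because no baseline gap is identified for that guide.

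**The case against.** The strongest reply is that nothing here is an error. The outcome and test are named, the t test on change is valid under randomisation, nobody dropped out, and the arms were similar at baseline. Preferring ANCOVA is a matter of efficiency, and the efficiency gain depends on a correlation the documents do not report. On the figures above the gain may be small: 0.03 of a shade unit at r = 0.3 and about 0.10 at r = 0.48, on a guide read in whole tabs. Colour is secondary, and reading non-significance as equality is a separate problem that ANCOVA does not cure. ANCOVA also assumes a common linear slope on baseline, which goes further than treating changes as roughly linear and may fit poorly where lightening is capped. Finally, the trial is complete, so the analysis adds comparisons made with results known.

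Most of this stands as a limit on the point's importance. It does not remove the point. A misspecified slope costs precision but does not bias a randomised comparison in any way that matters here. The worst case at r = 0 is an interval 1% to 2% wider. The post hoc status is met by labelling and by keeping the t test as the stated analysis.

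**Conclusion.** The concern holds as an optional improvement in precision, not as a flaw in validity. Baseline shade is held but used only by subtraction. Adjusting for it would narrow both colour intervals if |r| exceeds about 0.145 (0.12 to 0.19 for a baseline gap of 0 to 0.3 SD). For VITA Classical the half-width would fall from 0.91 to between 0.88 and 0.66 for r between 0.3 and 0.7.

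Narrowing is likely on the assumption that the reported baseline figures are VITA Classical units, since its absence would need final shade to be much more variable than baseline shade. It is not proved, because neither r nor the final SD is reported. The non-significant result is very unlikely to change, though that too cannot be proved without r. Confidence is medium.

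**What to change.** For each guide, add an ANCOVA of shade 1 week after the second session (or of the change) on arm, with baseline shade on the same guide as covariate. Report the adjusted difference and 95% CI beside the t test, together with r. Label the model post hoc and keep the t test as the stated analysis. Give baseline mean and SD separately for each guide, so that readers can relate change to starting shade; this is worth doing whatever r proves to be. Note that the covariate is entered linearly, building on the approximate linearity the plan already accepts for the scale and adding a common slope as a working assumption.

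The cost is one sentence in the analysis section, one model per guide on data already held, and one degree of freedom. If r = 0 the interval widens by about 1%, or 2% if the baseline gap were 0.3 SD.
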